Background information: The proposed 3-year adaptation and pilot testing of the Asian Women’s Action for Resilience and Empowerment (AWARE): A Stage IA and IB Intervention Development Study consists of the following goals: (1) provide the original Seeking Safety (SS) ¹ curriculum to Asian Women Discussion Group members for feedback and revision; (2) fully develop the AWARE protocol (which will modify SS by integrating Project FIO² and our cultural component) for API women; (3) use a pilot two-armed RCT design to test the feasibility and safety of our adapted intervention in Year 2, comparing the AWARE intervention group (n=48) with the wait-list group (n =48); and (4) employ multiple measures of the same constructs using a repeated measures design (assessments at pre-test, 8 weeks, and 3-month follow-up). We chose an RCT design to (1) establish the validity of statistical testing to the maximum level and (2) minimize potential biases (known and unknown factors and characteristics of the intervention and control groups). We will obtain outcomes for feasibility, safety, and preliminary efficacy of the primary outcomes (HIV-related outcomes) and secondary outcomes (psychiatric symptoms, substance use). These feasibility, safety, and efficacy outcomes will allow us to better plan for a larger-powered study. We will conduct the focus groups and pilot RCT at Boston University, School of Social Work (BUSSW), MA.

Study rationale and significance: *There is a mental and sexual health crisis in the API community in the US, particularly among young women (ages 18-35). This proposed*

project is intended to deepen our national understanding of this crisis and move us toward highly innovative solutions. We propose to design an appropriate intervention that reduces mental and sexual health problems in this population. There are 3 significant reasons why this study should be funded for research:

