3. Low reporting rates and under-utilization of treatment for traumatized API women. API women who were victims of sexual assault are particularly vulnerable. API women may experience higher levels of psychological distress or have fewer adaptive coping skills/social supports compared to sexually-victimized White women.³³ Rau and Diclemente found that API parents of sexual victims provide less support and minimal involvement in helping victims to seek evaluation and treatment with the appropriate services.³⁷ Our AWWHIP study showed that the experience of child sexual abuse combined with other types of abuse was the most powerful and robust predictor of severe depression, suicidal ideation, and suicide attempts.²⁶

Study objectives and/or hypotheses: The aim for *year one* is to adapt an intervention for API women that reduces HIV risk behaviors while increasing HIV knowledge and self-efficacy in negotiating safer sex (primary outcomes) and reduces psychiatric symptom severity and substance use (secondary outcomes). During *year 2*, the feasibility and safety of stage 1B of the AWARE intervention will be established through a pilot RCT, in which an intervention group will receive AWARE (n=48), which will have adapted SS by integrating Project FIO and

cultural components. During *years 2 and 3*, the preliminary efficacy of the intervention for API women will be tested.

It is hypothesized that the AWARE intervention group will significantly exceed the wait-list group in reduction of HIV risk behaviors and increased HIV knowledge and self-efficacy in negotiating safer sex at the 8 weeks and 3 months post-test points (primary outcomes). Additionally, the AWARE intervention group will significantly exceed the wait-list group in reduction of PTSD symptoms (and/or other mental health outcomes) and the frequency of substance use (at 8 weeks and 3 months post-test) (secondary outcomes).

Section E: Study subjects

E. 1. Gender

Select gender of subjects: ___ male female ___ both

E. 2. Age

Age range of subjects: (check all categories that apply to any of the subjects)

- Adults (18 years and older)
 Infants (< 1 year)
 Young children (1-6 years of age)
 Children 7-11 years
 Adolescents (12-17 years of age)

E. 3. Race/ Ethnicity (check all that apply)

- Mixed race or ethnicity
 American Indian or Alaskan Native
 Asian or Pacific Islander
 Black (not of Hispanic Origin)
 Hispanic
 White (not of Hispanic Origin)

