In Year 1 (the intervention development phase), we will begin recruiting and screening participants from AWARE. The first 10 women who pass the eligibility screenings and agree to participate the study will be invited to participate as members of the Asian Women Discussion Group, which will serve as a focus group. Although we will administer our preliminary AWARE intervention to the ten selected participants, there is no experimental intervention for the Asian Women Discussion Group. The sole purpose of this focus group is for members to give feedback from the perspective of AWARE intervention participants (as both the Asian Women Discussion Group and the AWARE group must meet the same demographic and clinical criteria). Members in this focus group will be ineligible to participate in the AWARE intervention group (Phase 2 of the study). Members in the Asian Women Discussion Group will attend 10 psychotherapy sessions and an additional discussion meeting afterward, as well as an additional session in September.

2) *AWARE intervention group*

In Year 2 of our study, using Asian Women Discussion Group’s feedback and other revisions made during the intervention development phase (in Year 1), we will administer our improved AWARE intervention (Stage IB) to 48 randomly-selected eligible participants. Participants in this group will receive 8 consecutive weekly sessions to receive the manualized intervention. After the last session, participants will be scheduled to return for a 3-month follow-up.

3) *Wait-list (or, delayed treatment) group*

Also in Year 2, the wait-list group will receive the exact same intervention 3 months *after* the start of the AWARE intervention group. The wait-list group will be comprised of 48 randomly-selected eligible participants.

Detailed Procedure:

1. In Year 1, for recruitment of Asian Women Discussion Group participants, we will use first use the database of 720 women who participated in the PI’s prior study (AWSHIP).

We will randomly select approximately 100 AWWSHIP women (who previously indicated interest in future studies) and ask them to participate in the initial eligibility screening. The function and purpose of Asian Women Discussion Group will be described to each woman by phone, letter, or email.

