6. In Year 2, we will recommence our recruitment efforts to identify and enroll eligible women into the intervention group and the wait-list group. The interviews during the screening process will be audio-recorded. Women who will be screened in Year 2 go through the same process as women who screened in Year 1 for Asian Women Discussion Group and must meet the same eligibility requirements (see Step 2 and Step 3).
7. Our goal is to screen about 400 women in Year 2. Of this number, we expect about 30% (n=120) to meet all eligibility criteria. We will randomly select 96 eligible women and assign 48 to the AWARE intervention group and 48 to the wait-list group.
8. Individual participation in the AWARE intervention group includes:
 - a. Written consent to participate including consent for the audiotaping of each session.
 - b. Completion of a baseline assessment prior to the start of the group sessions.
 - c. Participation in 105-minute group sessions each week (for a total of 8 weeks) with a small group of other participants and a clinician, covering topics including: Safety, Taking Good Care of Yourself, Compassion, Commitment, Creating Meaning, Setting Boundaries in Relationships, Coping with Triggers, Healthy Relationships, Self-Nurturing, and The Life Choices Game
 - d. \$26 payment and \$4 transportation reimbursement for each weekly group session and \$20 payment and \$4 transportation reimbursement for each assessment.
 - e. Completion of a weekly Adverse Events Log and a weekly questionnaire on the AWARE stories.
 - f. Receipt of and response to daily, secure mobile text messages (called “AWARE Stories”) in between each weekly session to reinforce participation and adherence
 - g. Completion of assessments upon the last intervention session
 - h. Completion of outcome assessments in a follow-up visit 3 months after the last intervention session
9. Individual participation in the wait-list group includes:
 - a. Written consent to participate including consent for the audiotaping of each session.
 - b. Completion of a baseline assessment prior to the start of the group sessions.
 - c. Participation in 90-minute group sessions each week (for a total of 8 weeks plus an additional post-intervention meeting) with a small group of other participants and a clinician, covering topics including: Safety, Taking Good Care of Yourself, Compassion, Commitment, Creating Meaning, Setting Boundaries in Relationships,

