The participants for the intervention program, Asian Women's Action for Resilience and Empowerment (AWARE) will be comprised of 106 women in total: 10 in the Asian Women Discussion focus group, 48 in the intervention group, and 48 in the wait-list group. The 10 women in Asian Women Discussion Group will participate in the focus group prior to the pilot randomized clinical trial (RCT). We will launch the AWARE campaign to reach out to API women in the greater Boston area and enroll eligible women in our study, using a two-armed randomized design: (1) a group that will receive the 10-session AWARE intervention (n=48) and (2) a wait-list control group who will receive no treatment (n =48). In order to successfully recruit the 96 AWARE participants, we estimate screening 500 women in the community.

G. 2. Sample size justification

Indicate why you chose the sample size proposed. Provide your sample size calculations. If this is a pilot study, this justification does not necessarily require a formal sample size calculation, but should provide a rationale for choosing the sample size proposed (e.g. to estimate a mean to a certain accuracy, to determine if the response rate is above a certain percentage, etc.) **Note: Once the IRB approves a certain study sample size then you may not enroll beyond that sample size without first obtaining approval from the IRB. ****** In determining your sample size be sure to allow for screen failures and study drop-outs in your calculations. Explain how many evaluable subjects you will need to end up with to answer your study question and how many subjects you will need to enroll and consent to achieve this number. The IRB counts study subjects a being enrolled once they have consented.

Our study is a pilot study which does not require a formal sample size calculation.

G. 3. Data Analysis

Provide a description of your plan for data analysis.

- State the types of comparisons you plan (e.g. comparison of means, comparison of proportions, regressions, analysis of variance).
- Which is the PRIMARY comparison/analysis?
- How will the analyses proposed relate to the primary purposes of your study?
- If you are doing qualitative research please state how comparisons will be made.

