Quantitative data for protocol evaluation and participant psychometric monitoring: We will evaluate participants in the Asian Women Discussion Group by comparing the results of pre-intervention and post-intervention psychometric measures. These comparisons will be used to determine if the current protocol is achieving the intervention's goals of providing benefits to participant's mental and behavioral health.

Data Analysis for Aim 2 (year 2):

(1) Feasibility Analysis of group psychotherapy: We conservatively anticipate that 15% of participants will dropout during the 8 week RCT. We also anticipate that another 5% will dropout at the 3-month follow-up evaluation. The first stage of analysis will involve estimating the proportion of women who are eligible and agree to enroll in the study. A 95% confidence interval for the proportion will also be produced. Then, among those who enroll, baseline characteristics will be compared between those randomized to the intervention and those randomized to the wait-list control group to assess balance.

We will estimate the proportion of women who adhere at 8 weeks and 3-month follow-up. Mean proportion of women who attend (at 8 weeks and 3-month follow-up) and 95% confidence intervals will be generated for the total sample and then by groups. We will test the

difference between the participants' adherence rates in the intervention and control group at 8 weeks and 3-month follow-up using a chi-square test. We will then examine bivariate associations between baseline characteristics and attrition (each time point considered separately) using chi-square tests for categorical variables and two sample t tests for continuous variables among all participants. Multivariable associations will be examined using multiple logistic regression models for adherence by group, relating those characteristics that were significant in bivariate analysis to attrition, if sample size permits.

(2) Feasibility Analysis of AWARE Stories (Hypothesis for secure mobile messaging): Higher level of satisfaction and higher utilization of secure text messages are positively associated with group psychotherapy attendance. Ordinal chi-square tests will be used to examine the association between ordinal scale (1-4) of messaging satisfaction and utilization questions and psychotherapy attendance.]

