Evaluation of Pilot RCT Analysis: We will use an intention-to-treat (ITT) analysis, which indicates all women who are randomized will be included for analysis. To test the success of the randomization, prognostic factors including baseline education, psychiatric diagnosis severity, and substance use will be compared between participants in the intervention group and wait-list group using chi-square tests. Baseline characteristics that show imbalance between groups will be adjusted in multivariate regression models. The efficacy outcome variables will be analyzed as either dichotomized or continuous variables. For PTSD, continuous measures of the CAPS will be assessed. In order to sensitively capture any changes in PTSD scores, continuous measure will be chosen. For HIV outcomes, we will use both dichotomous and continuous variables to measure status and severity of the outcomes at baseline, 8 weeks, and 3-month post-test. Mixed effects models will be used to compare the pattern of change in dichotomous and continuous outcomes over time between groups using normal and logit links, respectively. We will first use an unstructured covariance matrix to account for correlation between repeated measurements in the same participant and compare it to other covariance structures, using goodness of fit. The most suitable covariance matrix will be chosen for the final model. The same approach will be followed for secondary outcomes. All statistical testing will be performed at the significance level of 0.05 using SAS 9.3.102. Additionally, in order to explore whether compliance affects outcome measures, we will compare the sexual risk behavior, psychiatric severity, and substance use measures between those who drop out versus those who complete the intervention using two-tailed, independent samples t-tests.

Section H: Potential Risks/ Discomforts

H.1. Description of Risks or Discomforts

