All sessions will be led by a licensed therapist. These sessions will be recorded and safely stored in a password-protected server, and therapists will work closely with and be monitored by the principal investigator. Participants will be asked to read and sign statement of informed consent explaining privacy protections and confidentiality protections. If participants experience discomfort and wish to discontinue the treatment, they will be able to withdraw from the study or refuse to complete a session. Additionally, if participants begin to show symptoms of depression, self-harm, or suicidality, that the therapist leading the group believes warrants treatment they will be withdrawn from the study and referred to a hospital for alternative treatment, which includes treatment at BU Medical Center (BUMC), South Cove Community Health Center, or South Shore Mental Health, the latter two where we have advisors ([name] and [name]).

During the course of each SS session, the therapist will take note of each participant to ensure that none exhibit traits of a deteriorating condition. Participants in crisis (e.g. exhibiting symptoms of imminent risk to self or others, psychotic symptoms, safety concerns) will be immediately referred to a hospital to ensure proper treatment and safety. Participants who are not deemed to be in an emergency situation but are showing symptoms of deterioration (as determined by the licensed therapist) will be closely monitored and, if appropriate, considered for referral for alternative treatment. All decisions will be made jointly by the therapist and the principal investigator.

“AWARE Stories” via secure mobile messaging. We aim to enhance the quality of our mental health intervention by supplementing it with a secure messaging application. We will write and use text messages that are closely tied with our weekly session topics to stimulate aspects of psychotherapy outside the weekly group sessions. We will utilize Doc Halo, a secure mobile messaging application, and SMS as message delivery platforms. Participants will be given the

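### The efficacy models allow for correlation within a woman but not within the therapy groups in which AWARE is delivered, so week-8 standard errors may be too small

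*Protocol*

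**What the plan says.** Women are randomised individually, 48 to AWARE and 48 to wait-list (Protocol F.4, step 7). Step 8c describes AWARE as "Participation in 105-minute group sessions each week (for a total of 8 weeks) with a small group of other participants and a clinician", and H.1 adds: "All sessions will be led by a licensed therapist". F.4 says that "the wait-list group will receive the exact same intervention 3 months" after the AWARE arm starts, so no wait-list woman has attended a session by week 8.

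The analysis is set out in G.3, in identical text under Aims 2 and 3. Mixed effects models compare the arms' pattern of change, and all tests use a 0.05 level. On dependence the text says: "We will first use an unstructured covariance matrix to account for correlation between repeated measurements in the same participant". Other covariance structures are then compared by goodness of fit and the most suitable is kept. The document contains no term for therapy group or therapist, no cluster-robust variance and no ICC.

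**The concern.** Women are randomised one by one but treated together in one arm only, which is a partially nested design. Women in one therapy group share a therapist, eight weekly sessions and each other's contributions, so their week-8 outcomes may be correlated. The covariance matrix in G.3 describes one woman's visits. Choosing another structure for that matrix changes how her own measurements relate to each other and cannot introduce correlation between women.

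Section D hypothesises that "the AWARE intervention group will significantly exceed the wait-list group in reduction of HIV risk behaviors and increased HIV knowledge", with week 8 among the time points, and G.3 tests this at 0.05. If outcomes correlate within therapy groups, the week-8 intervals are too narrow and the p-values too small. Section D also states the use of the results: "These feasibility, safety, and efficacy outcomes will allow us to better plan for a larger-powered study". Overstated precision would feed into that planning.

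**Working it through.** The protocol has no power, sample-size or design-effect figure to reproduce; G.2 says a pilot needs no formal calculation.

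**Inputs from the protocol:** 48 women per arm (F.4, step 7); significance level 0.05 (G.3), taken as two-sided because the efficacy text does not say; 15% dropout by week 8 (G.3, Aim 2: "We conservatively anticipate that 15% of participants will dropout during the 8 week RCT"); only the AWARE arm grouped at week 8 (F.4).

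**Assumptions, not in the protocol:** m = 6 to 12 women per therapy group, giving 48/12 = 4 to 48/6 = 8 groups; ICC = 0.01 to 0.10, meaning the ICC of the analysed week-8 quantity; equal total variance in both arms.

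**Formulas:**
- Design effect in the AWARE arm: DE = 1 + (m − 1) × ICC. It is 1 in the wait-list arm.
- True SE / model SE = √((DE + 1)/2).
- Actual two-sided error = 2 × (1 − Φ(1.96 / ratio)).

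For m = 8 and ICC = 0.05: DE = 1 + 7 × 0.05 = 1.35; ratio = √(2.35/2) = 1.084; 1.96/1.084 = 1.808; error = 0.071.

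| m | ICC | DE | SE ratio | Actual error |
|---|---|---|---|---|
| 6 | 0.01 | 1.05 | 1.012 | 0.053 |
| 6 | 0.05 | 1.25 | 1.061 | 0.065 |
| 6 | 0.10 | 1.50 | 1.118 | 0.080 |
| 8 | 0.01 | 1.07 | 1.017 | 0.054 |
| 8 | 0.05 | 1.35 | 1.084 | 0.071 |
| 8 | 0.10 | 1.70 | 1.162 | 0.092 |
| 12 | 0.01 | 1.11 | 1.027 | 0.056 |
| 12 | 0.05 | 1.55 | 1.129 | 0.083 |
| 12 | 0.10 | 2.10 | 1.245 | 0.115 |

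If every group shrinks by 15% (m × 0.85):

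| m | ICC | DE | SE ratio | Actual error |
|---|---|---|---|---|
| 5.1 | 0.01 | 1.041 | 1.010 | 0.052 |
| 6.8 | 0.05 | 1.29 | 1.070 | 0.067 |
| 10.2 | 0.10 | 1.92 | 1.208 | 0.105 |

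**Simulation of the unadjusted test** (48 per arm, one time point, continuous outcome, no true effect, 40,000 trials per cell): error 0.053 at m = 6, ICC 0.01; 0.070 at m = 8, ICC 0.05; 0.116 at m = 12, ICC 0.10. These agree with the formula.

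**Simulation with baseline adjustment** (assumed baseline correlation 0.5, 20,000 trials per cell): 0.078 at m = 8, ICC 0.05 and 0.136 at m = 12, ICC 0.10; 0.048 to 0.051 when the ICC is zero. The higher errors arise because the ICC there is a share of total variance. Adjustment leaves 1 − 0.5² = 0.75 of that variance, so 0.05 becomes 0.05/0.75 = 0.067 on the analysed scale. The formula then gives DE = 1.467, ratio 1.111 and error 0.078.

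**The remedy, tested on a stand-in.** A Satterthwaite test of AWARE group means against individual wait-list women had error of about 0.05 to 0.058 over m = 6, 8, 12 and ICC 0.01, 0.05, 0.10.

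**3-month visit.** No figure is given. Wait-list women may have attended sessions by then, and F.4 and G.1 do not settle when they are assessed.

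**The case against.** **The size is not in the document.** This is correct. Without group size, number of therapists or ICC, the effect runs from negligible to more than double the nominal error, and nothing in the protocol shows where this trial falls.

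**G.3 is a summary box on an ethics form, and a statistical analysis plan may add the term.** This stands in part. Mixed models can be extended, and G.3 does not exclude a group effect. Details such as the degrees-of-freedom method would normally go in that plan. But G.3 does state the model, the correlation it accounts for, the rule for choosing the covariance and the test level. A plan that specific, followed as written, leaves therapy group out.

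**The figures are for one week-8 contrast of a continuous outcome, whereas the planned model covers three visits and also dichotomous outcomes.** This is true and limits the figures to that contrast. Section D does make week 8 one of its hypothesised time points.

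**Little depends on it, and the correction has a price.** The trial is a pilot with preliminary efficacy, and no confirmatory decision rests on it. With 12 per group, hence only four groups, the adjusted intervals are about 14% wider at ICC 0.01, where the true inflation is 2.7%, and 29% wider at ICC 0.05, where it is 13%. The excess comes from having few degrees of freedom. That trade-off is real.

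**The remedy is only partly tested.** The simulation was not a REML mixed model, and the logit version with 4 to 8 groups was not checked. The zero-variance rule tested was a fallback to the unadjusted test, which had error 0.036 to 0.049. It is not identical to keeping the adjusted result, although a mixed model whose group variance is zero should have nearly the same standard error.

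**Conclusion.** The concern holds as a conditional statement: for any ICC above zero and more than one woman per therapy group, the model in G.3 understates the week-8 between-arm standard error. With 6 to 12 women per group and ICC 0.01 to 0.10, the true standard error is 1% to 25% larger than reported and the actual error is 5.3% to 11.5%. With 15% dropout the ranges are 1% to 21% and 5.2% to 10.5%. The omission is plain from the text; its size depends on two quantities that the protocol does not give. It should be corrected because the change is small and the results are meant to inform a larger trial, but the pilot's feasibility aims do not depend on it. Nothing is claimed for the 3-month visit.

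**What to change.** In both copies of the efficacy text in G.3:

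- State that each woman's therapy group is recorded.
- Add a therapy-group random effect at post-treatment visits, not at baseline. At week 8 it applies to the AWARE arm only, with wait-list women as singletons.
- For continuous outcomes, use Kenward-Roger or Satterthwaite degrees of freedom. For dichotomous outcomes, put the same term in the logit model and say that small-sample inference is approximate.
- Name the group-adjusted result as the reported one. If the group variance is estimated as zero, say so, keep that result and show the unadjusted one as a sensitivity analysis.
- Report the ICC with its confidence interval and call it imprecise.
- For the 3-month visit, first state when wait-list women are assessed, then apply the term to whichever arm has had sessions by then.

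The cost is revised wording and one variable. K.1 mentions only an individual ID, but sessions are recorded and paid per session, so group membership is probably known operationally. Intervals will be wider: in simulation 5% (6 per group, ICC 0.01), 16% (8 per group, ICC 0.05) and 47% (12 per group, ICC 0.10). With 4 to 8 groups, the group variance will be estimated as zero or below in about 25% to 55% of trials (28% to 55% with 15% dropout).

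A separate editorial point, which adds no weight: the same text pairs the links with the outcome types in reverse order. It should read logit link (binomial) for dichotomous outcomes and identity link (normal) for continuous ones.
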